Study Duration	52 to 58 weeks for subjects randomized to TEOSYAL® RHA Redensity treatment group, and 60 to 66 weeks for subjects randomized to the “No-Treatment” control group	Number of Subjects	At least 200 subjects, 150 treated and 50 No-Treatment controls
Treatment Groups	
Subjects will be randomized (3:1 ratio) to one of the following groups:
 
 • TEOSYAL® RHA Redensity • No-Treatment control 		
Study Design	
This is a randomized, blinded, No-Treatment control, multicenter, prospective clinical study, to identify whether TEOSYAL® RHA Redensity is more effective than No-Treatment in the correction of moderate to severe perioral rhytids at Week 8 after last treatment.
 
The Treating Investigator (TI) at screening will evaluate the subject’s perioral rhytids severity using the Perioral Rhytids Severity Rating Scale (PR-SRS) for eligibility of the subject for the study.
 
The Blinded Live Evaluator (BLE) at screening will evaluate the subject’s perioral rhytids severity using the PR-SRS in order to confirm eligibility and to establish a pre-treatment score for assessment of effectiveness. This will be done independently of the TI, and exact concordance between the BLE and the TI is not necessary for eligibility of the subject for the study.
 
Enrolled subjects will be randomized to either the TEOSYAL® RHA Redensity treatment group or the “No-Treatment” control group. The TI will administer study device, and if necessary, subjects will receive a touch-up treatment 14 days following the initial treatment to optimize the results. The TI will conduct safety and effectiveness evaluations at study visits, which will occur at Week 4, 8, 12, 16, 24, 36, and 52 after the last treatment, and 4 weeks after a repeat treatment.
 
A Blinded Live Evaluator (BLE) will conduct assessments of efficacy during the trial, including assessment of the primary endpoint at Week 8 after the last treatment. The BLE will conduct effectiveness evaluations at Week 8, 12, 16, 24, 36, and 52 after the last treatment.
 
All subjects will be followed for 52 weeks after initial treatment or touch-up, at which point they will be offered retreatment (provided that the TI deems the treatment to be appropriate and the subject agrees) and will then be followed for 4 weeks after retreatment before exiting the study. If a subject has returned to his pre-treatment PR-SRS score at Week 12 or Week 16 or Week 24 or Week 36 after initial treatment or touch up (as assessed by the TI), subject will be eligible for optional early retreatment if necessary at 12 or 16 or 24 or 36 weeks after baseline (provided that the TI deems the treatment to be appropriate, and the subject agrees). The subject will then be
		

	
followed for an additional 4 weeks after repeat treatment and for all subsequent scheduled visits. Subjects receiving optional early retreatment at Week 12 or Week 16 or Week 24 or Week 36 after the after initial treatment or touch-up, will be offered retreatment at Week 52.
 
Subjects randomized to the “No-Treatment” control group will receive their first treatment after the primary endpoint evaluation (Week 8 after randomization) and will then follow the same schedule as the initial treatment group.

Hypothesis	TEOSYAL® RHA Redensity will be superior to No-Treatment control for the correction of moderate to severe perioral rhytids as determined by the PR-SRS at Week 8 after the last treatment. An improvement in the PR-SRS of ≥ 1 -grade compared to pre-treatment will be considered clinically meaningful.
Objectives	To establish the safety and effectiveness of TEOSYAL® RHA Redensity in the treatment of moderate to severe perioral rhytids.
Inclusion Criteria	
1. Outpatient, male or female of any race, 22 years of age or older. Female subjects of childbearing potential must have a negative UPT at Visit 1 and practice a reliable method of contraception throughout the study. [REDACTED]3. Willing to abstain from facial aesthetic procedures/therapies that could interfere with study evaluations (e.g., other fillers, botulinum toxin injections, laser or chemical resurfacing, etc.) for the duration of the study [REDACTED]4. Able to follow study instructions and complete all required visits.5. Sign the IRB-approved ICF, Photographic Release Form and the Authorization for Use and release of Health and Research Study Information (HIPAA) form prior to any study-related procedures being performed.
Exclusion Criteria	
1. Female subjects that are pregnant, breast-feeding, or of childbearing potential and not practicing reliable birth control.2. Known hypersensitivity or previous allergic reaction to any component of the study devices. [REDACTED]4. Known sensitivity to local anesthetics of the amide type, history of multiple severe allergies, or history of anaphylactic shock. [REDACTED]6. Clinically significant active skin disease within 6 months prior to study entry (TI discretion). [REDACTED]8. History of connective tissue disease. [REDACTED]10. Need for clinically significant (TI discretion) and continuous medical treatment within 2 weeks prior to Visit 1. [REDACTED]12. Herpes simplex lesion flare-ups greater than 6 per year. [REDACTED]14. Elective, clinically significant facial procedures that may confound the interpretation of the results in the perioral region (TI discretion), prior to study enrollment.

[figure not shown]
	
16. Subjects with known prolonged bleeding times because of disease or medication. If on a drug or supplement that prolongs bleeding times (eg non-steroidal anti-inflammatory, anti-coagulant, fish oil), wait 14 days or until bleeding times return to normal before injecting.
 
18. Have dentures or any device covering all or part of the upper palate, and/or severe malocclusion, dentofacial or maxillofacial deformities, or significant asymmetry of the perioral area (TI discretion).
 
20. Exposure to any other investigational drug/device within 90 days of entering the study.
 
21. [REDACTED]

Device Administration	[REDACTED] [REDACTED] [REDACTED] [REDACTED]
Blinding	The BLE will be blinded to the treatment allocation. Furthermore, to ensure that they remain masked and unbiased when making their assessments throughout the study, the BLE, TI and subject will not be allowed to refer to each other's efficacy assessments. All subjects will be instructed to not discuss their study treatment, AEs, or CTRs with the BLE.
Visit Procedures	[REDACTED]
Efficacy Evaluations	[REDACTED] [REDACTED] [REDACTED] [REDACTED] [REDACTED] • [REDACTED]
Safety Evaluations	
• Adverse Events.• Post-injection common treatment response [REDACTED]

	
• Assessments of lip function;• Assessment of Injection Site Pain
Primary Endpoint	
The primary endpoint will be a co-primary endpoint. A responder will be defined as a subject who has a ≥ 1-grade improvement on the PR-SRS as assessed by the BLE before initial treatment and at Week 8 after initial treatment or touch-up. Only data from the first 8-week phase will be taken into account. The No-Treatment control group after treatment will not be pooled for the primary endpoint.
 
The effectiveness of TEOSYAL® RHA Redensity will be demonstrated if:
 
• The responder rate for subjects treated with TEOSYAL® RHA Redensity is statistically superior to the responder rate for the No-Treatment control, and;• The responder rate for subjects treated with TEOSYAL® RHA Redensity is $\geq 70\%$, and;• The difference between the responder rate for subjects treated with TEOSYAL® RHA Redensity and the No-Treatment group must be ≥ 50 points.
Secondary Endpoints	
For the Secondary Endpoints, like for the Primary Endpoint, only data from the first 8-week phase will be taken into account, and will compare TEOSYAL® RHA Redensity to No-Treatment (the No-Treatment control group after treatment will not be pooled):
 
• [REDACTED]• [REDACTED]• [REDACTED]• [REDACTED]
Sample Size	
In order to have the study able to detect any AE that has an incident rate of 2.5% or more in the sub-population of subjects of Fitzpatrick skin type IV to VI, at least 160 subjects should be enrolled and treated with the investigational device in the two pooled arms. With an anticipated 20% drop-out rate throughout the entire study, a minimum total sample of 200 subjects ($160 / 0.8 = 200$), who will each receive TEOSYAL® RHA Redensity are required in order to detect a sufficient AE rate.
 
[REDACTED]

Statistical Methods	
Primary Endpoint: The primary endpoint will be analyzed in a superiority statistical model using the PR-SRS as rated by the BLE. A responder is defined as a subject with a ≥ 1-grade improvement on the PR-SRS as assessed by the BLE at Week 8 after initial or touch-up compared with the pre-treatment assessment (baseline) by the BLE. Only data from the first 8-week phase will be taken into account (the No-Treatment control group after treatment will not be pooled for the primary endpoint).
 
[REDACTED]

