4 OVERVIEW OF STUDY DESIGN

4.1 Study Design

This is a randomized, blinded, No-Treatment control, multicenter, prospective clinical study, to identify whether TEOSYAL® RHA Redensity is more effective than No-Treatment in the correction of moderate to severe perioral rhytids at Week 8 after initial or touch-up treatment.

The **Treating Investigator** (TI) will evaluate subjects for eligibility of the subject for the study. The **Blinded Live Evaluator** (BLE) at screening will evaluate the subject's perioral rhytids severity using the Perioral Rhytids Severity Rating Scale (PR-SRS) in order to confirm eligibility and to establish a pre-treatment score. This will be done independently of the TI, and exact concordance between the BLE and the TI is not necessary.

Enrolled subjects will be randomized to either the TEOSYAL® RHA Redensity treatment group or the “No-Treatment” control group. The TI will administer study device, and if necessary, subjects will receive a touch-up treatment 14 days following the initial treatment to optimize the results. The TI will conduct safety and effectiveness evaluations at study subject visits, which will occur at Week 4, 8, 12, 16, 24, 36, and 52 after initial or touch-up treatment, and 4 weeks after a repeat treatment.

The BLE will conduct assessments of efficacy during the trial, including assessment of the primary endpoint at Week 8 after initial or touch up treatment. The BLE will conduct effectiveness evaluations at Week 8, 12, 16, 24, 36, and 52 after initial or touch-up treatment.

Subjects will be followed for 52 weeks from initial or touch up treatment, at which point they will be offered a repeat treatment (provided that the TI deems the treatment to be appropriate, and if the subject agrees). The subject will then be followed for an additional 4 weeks after the treatment before exiting the study.

[figure not shown]
Should a subject return to his/her pre-treatment PR-SRS level before Week 52, as assessed by the TI, he/she will be eligible to receive an early repeat treatment (provided that the TI deems the treatment to be appropriate, and if the subject agrees) at Week 12, or Week 16, or Week 24, or Week 36 after initial or touch-up treatment. .

Subjects randomized to the “No-Treatment” control group will receive their first treatment after the primary endpoint evaluation (8 weeks after randomization) and will then follow the same schedule as the initial treatment group.

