11.5 Sample Size Considerations

[REDACTED]

The study will ensure that enrolled subjects are representative of U.S. population ethnicity and will be comprised of at least 25% subjects of Fitzpatrick skin IV to VI. In order to be able to detect a sufficient AE rate (i.e., maximum 2.5% in the sub-population of subjects of Fitzpatrick skin type IV to VI), the number of subjects must be increased beyond that required for achieving statistical power for the primary efficacy outcome; specifically:

[REDACTED]

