11.8 Safety Analysis

[REDACTED]

[REDACTED]

The study will be able to detect any AE that has an incident rate of <1.0% (0.625%) or more (assuming 200 subjects will be treated with the investigational device in the two pooled arms and taking [REDACTED]

[REDACTED]

[REDACTED]

[REDACTED]

[REDACTED]

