### 7.1.1 Intent-to-Treat (ITT) Population

### 7.1.2 Per Protocol (PP) Population

#### 7.1.2.1 Safety (SAFT) Population

The SAFT Population will consist of all subjects in the No-Treatment control group, and all subjects in the Redensity treatment group that are randomized and received at least one treatment with a study device. Subjects in the SAFT Population will be analyzed in the group of the treatment they actually received, whether or not it is the group to which they are randomized.

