## 8. SAMPLE SIZE JUSTIFICATION

The study will ensure that enrolled subjects are representative of U.S. population ethnicity and will be comprised of at least 25% subjects of Fitzpatrick skin IV to VI. In order to be able to detect a sufficient AE rate (i.e., maximum 2.5% in the sub-population of subjects of Fitzpatrick skin type IV to VI), the number of subjects must be increased beyond that required for achieving statistical power for the primary efficacy outcome; specifically:

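### The 2.5% and 0.625% adverse-event detection limits are rates at which one case is expected; at minimum enrolment the chance of seeing any case at those rates is about 63% to 72%

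*Protocol*

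**What the plan says.** The Sample Size row of the Protocol Synopsis gives the aim that the study be "able to detect any AE that has an incident rate of 2.5% or more in the sub-population of subjects of Fitzpatrick skin type" (the types meant are IV to VI). For this it requires that "at least 160 subjects should be enrolled and treated with the investigational device in the two pooled arms". It then divides by 0.8 for an anticipated 20% drop-out over the whole study and arrives at a minimum of 200.

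Protocol 11.5 states that the enrolled population "will be comprised of at least 25% subjects of Fitzpatrick skin IV to VI". It gives the safety aim as being able to "detect a sufficient AE rate (i.e., maximum 2.5% in the sub-population of subjects of Fitzpatrick skin type IV to VI". SAP 8 repeats this and says that, for that purpose, "the number of subjects must be increased beyond that required for achieving statistical power for the primary efficacy outcome". In both places the detail that follows is redacted or missing.

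Protocol 11.8 adds an overall figure: "The study will be able to detect any AE that has an incident rate of <1.0% (0.625%) or more". The sentence assumes 200 treated subjects in the two pooled arms, and its end is redacted.

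No readable sentence attaches a probability or a confidence level to detection.

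**The concern.** Read plainly, the Synopsis and Protocol 11.8 say that any adverse event at or above the stated rate will be picked up. If the stated rates are only those at which one case is expected, an event at the limit will quite often not be seen at all.

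The subgroup target is the stated reason for going beyond the efficacy sample size, so it should say accurately what the design delivers. A reader who takes it as reliable detection could treat zero cases in Fitzpatrick IV to VI as excluding a 2.5% rate. Zero cases at these subgroup sizes would still be compatible with clearly higher rates.

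**Working it through.** **Inputs.** 160 treated subjects, 20% drop-out, total 200 and the 2.5% target come from the Protocol Synopsis. The minimum 25% share of Fitzpatrick IV to VI comes from Protocol 11.5 and SAP 8. The 0.625% figure comes from Protocol 11.8.

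**Reproducing the plan's figures.**
- 160 / 0.8 = 200, as stated.
- Subgroup after drop-out: 0.25 × 160 = 40, and 1/40 = 2.5%, as stated.
- Overall after drop-out: 1/160 = 0.625%, as stated.
- Other rules do not reproduce the pair. Without drop-out, 1/50 = 2.0% and 1/200 = 0.5%. The rule of three gives 3/40 = 7.5% and 3/160 = 1.875%. An 80% chance of at least one case gives 3.94% (n=40) and 1.00% (n=160).

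The one-expected-case rule is therefore an inference, but it fits both figures exactly.

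**Chance of at least one case**, 1 − (1 − p)^n:

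| Group | Rate p | n | Expected cases | At least one case | No case |
|---|---|---|---|---|---|
| Fitzpatrick IV–VI | 2.5% | 40 | 1.00 | 63.7% | 36.3% |
| Fitzpatrick IV–VI | 2.5% | 50 | 1.25 | 71.8% | 28.2% |
| All treated | 0.625% | 160 | 1.00 | 63.3% | 36.7% |
| All treated | 0.625% | 200 | 1.25 | 71.5% | 28.5% |

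The values 40 and 160 remove the full 20% drop-out. The values 50 (0.25 × 200) and 200 count everyone at minimum enrolment. The latter requires every control to reach treatment, and controls "will receive their first treatment after the primary endpoint evaluation (8 weeks after randomization"), so a control who leaves before then is never exposed. As an illustration only, if 10 of 50 controls left before first treatment, 190 would be treated and the overall figure would be 1 − 0.99375^190 = 69.6%.

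**Away from the limit.** Detection improves with a higher rate or a larger subgroup:
- Subgroup rate of 4%, n=40: 1 − 0.96^40 = 80.5%.
- Overall rate of 1.0%: 80.0% (n=160) and 86.6% (n=200).
- Subgroup rate of 2.5%, n=64 (64/200 = 32%): 1 − 0.975^64 = 80.2%.

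**Rate seen at least once with a given probability**, 1 − 0.20^(1/n) for 80% and 1 − 0.05^(1/n) for 95%:

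| n | 80% | 95% |
|---|---|---|
| 40 | 3.9% | 7.2% |
| 50 | 3.2% | 5.8% |
| 160 | 1.0% | 1.9% |
| 200 | 0.8% | 1.5% |

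The 95% column is also the exact one-sided 95% upper limit when no case is seen: 0/40 is compatible with a true rate up to 7.2%, and 0/50 with up to 5.8%.

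**The case against.** The strongest reply is that the meaning of detection may lie in redacted text. Protocol 11.5 and SAP 8 break off where the derivation should follow, and Protocol 11.8 is cut mid-sentence. If that text defines detection as one expected case, the plan's figures do what it says. This stands in part: no omission and no calculation error can be alleged. But no definition changes the probabilities above, and the readable sentences in the Synopsis and Protocol 11.8 carry no qualifier.

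The lower values are also pessimistic for some events. Drop-out is spread over the whole study, and most subjects are treated at the start. For events soon after injection most later drop-outs still contribute, so the chance is nearer the upper values. This stands.

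Further, no readable test, stopping rule or success criterion depends on these rates, and the 80% and 95% levels above are benchmarks chosen here, not levels the plan promises. This stands too, and it is why the point is minor.

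Some stronger readings are tempting but not supported:
- *Both rates set the sample size.* Only the 2.5% subgroup target does; 0.625% appears only in Protocol 11.8, as a reported consequence.
- *About 72% is a ceiling.* Both the 200 subjects and the 25% share are minimums, so the chance is higher if either is exceeded.
- *The claim fails at all rates, or more subjects are needed.* Detection is better above the limits, and no readable text promises a probability that 200 subjects fail to reach.
- *Never-treated controls dilute the safety denominator*, because the SAP safety population includes "all subjects in the No-Treatment control group, and all subjects in the Redensity treatment group that are randomized and received at least one treatment". The same SAP section analyses subjects by the treatment actually received, which keeps untreated controls out of the treated group.

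**Conclusion.** The point holds, with minor severity. The Synopsis and Protocol 11.8 state a detection property that the design does not have at its own lower limits. At minimum enrolment and the minimum subgroup share, an event occurring at 2.5% in Fitzpatrick IV to VI would go unseen with probability 28% to 36%. An event at 0.625% overall would go unseen with probability 29% to 37%.

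This rests on three assumptions: independent subjects with a common event rate, a subgroup at its 25% minimum, and between 160 and 200 subjects contributing. That the rates were obtained as one expected case is inferred from two exact matches; the probabilities do not depend on that inference. The sample-size arithmetic is correct, and 200 subjects can stand.

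**What to change.** Keep 200 subjects and change the wording.

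1. **Protocol Synopsis.** State that 2.5% is the rate at which one case is expected among 40 Fitzpatrick IV to VI subjects. The chance of at least one case is then about 64% (about 72% with 50). Rates seen at least once with 80% / 95% probability are 3.9% / 7.2% (n=40) or 3.2% / 5.8% (n=50).
2. **Protocol 11.8.** State that 0.625% is the rate at which one case is expected among 160 subjects. The chance of at least one case is then about 63% (71.5% with 200). Rates seen with 80% / 95% probability are 1.0% / 1.9% (n=160) or 0.8% / 1.5% (n=200).
3. **Protocol 11.5 and SAP 8.** Align these only if their redacted text does not already say the same.
4. **Optional.** Unless the redacted tables already do so, report exact one-sided 95% upper limits for key adverse events with zero cases among treated subjects, overall and in Fitzpatrick IV to VI.

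The cost is a less favourable stated detection limit and, if item 4 is taken up, a little extra output. No subjects are added, and no endpoint, test, population or decision rule changes.

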A horizontal bar chart with 20 categories on the y-axis and a count of samples on the x-axis. The x-axis ranges from 0 to 1000 with major ticks every 100 units. Each category is represented by a black bar. The distribution is highly right-skewed, with most categories having fewer than 100 samples. Category 1 has the highest count, followed by Category 10, Category 19, and Category 20.

Category	Count
1	950
2	100
3	100
4	100
5	100
6	100
7	100
8	100
9	100
10	100
11	100
12	100
13	100
14	100
15	100
16	100
17	100
18	100
19	100
20	100

1 INTRODUCTION

1.1 Background

[REDACTED]

[REDACTED]

[REDACTED]

[REDACTED]

[REDACTED]

[REDACTED]

[REDACTED]

[REDACTED]

[REDACTED]

1.2 Rationale for Study

[REDACTED]

1.3 Hypothesis

TEOSYAL® RHA Redensity will be superior to No-Treatment control for the correction of moderate to severe perioral rhytids as determined by the PR-SRS at 8 weeks after initial or touch-up treatment. An improvement in the PR-SRS of ≥ 1 -grade from pre-treatment will be considered clinically meaningful.

2 STUDY OBJECTIVES

The study objectives are to establish the safety and effectiveness of TEOSYAL® RHA Redensity in the treatment of moderate to severe perioral rhytids:

1. To demonstrate the superiority of TEOSYAL® RHA Redensity versus the No-Treatment control at 8 weeks for the correction of moderate to severe perioral rhytids. Assessment of superiority will be based on the Perioral Rhytids Severity Rating Scale (PR-SRS) as rated by the Blinded Live Evaluator (BLE) at each investigative site.
2. To evaluate the safety of TEOSYAL® RHA Redensity for the treatment of moderate to severe perioral rhytids. Safety will be determined by the rates of Adverse Events (AEs) associated with the use of the study device. Subjects will be observed for up to approximately 52 weeks following initial treatment or touch-up treatment with the study device. Safety will also be evaluated for 4 weeks following any retreatment.

3 COMPLIANCE STATEMENT

The study will be conducted in accordance with the protocol, International Conference on Harmonization (ICH) and Good Clinical Practice (GCP), the Declaration of Helsinki, United States (US) Code of Federal Regulations (CFR) applicable to clinical studies (45 CFR Part 46, 21 CFR Part 50, 21 CFR Part 56, and 21 CFR Part 312). In addition, the study will be conducted in compliance with all applicable laws and regulatory requirements relevant to the use of new medical devices in the United States and in Canada.

The sites' Principal Investigator (also referred to as the Treating Investigator [TI], both terms are used interchangeably) is responsible for ensuring the privacy, safety and welfare of the subjects during and after the study, and must ensure that personnel trained in its proper use are immediately available in case of a medical emergency. The Investigators (BLE and TI) must be familiar with the background and requirements of the study and with the properties of the study device as described in the Investigator's Brochure and package inserts. The Principal Investigator at each site has the overall responsibility for the conduct and administration of the study at their site, and for contact with study site management, and local authorities. [REDACTED]

[REDACTED]

